4.11.1. Asparaginase Activity and Amino Acids

Missing asparaginase activity data will not be replaced or imputed.

Similar rules will be followed for calculating ASN and GLN levels.

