Asparaginase has a central part of the treatment of childhood ALL. Asparaginase is an enzyme that hydrolyses asparagine to aspartic acid and ammonia and, to some extent, glutamine to glutamic acid and ammonia (4). In the extra cellular space this results in asparagine depletion and a reduction of glutamine. The lymphoblasts, which cannot effectively synthesize *de novo* asparagine, have their protein biosynthesis inhibited, and they undergo apoptosis (5). Cerebrospinal fluid (CSF) asparagine depletion is considered as a marker of asparaginase effect in the central nervous system (CNS) and asparaginase play an important role in CNS-directed anti-leukemia therapy(6).

In the current NOPHO ALL 2008 protocol, PEG-asparaginase (pegylated E.coli asparaginase) is for non-high risk (non-HR) patients given from treatment week 5 to 35, being given at a dose of 1000 IU/m² i.m. every two weeks. Children and adults (aged 1-45 years) in five Nordic and two Baltic countries (Lithuania and Estonia) are treated according to ALL2008. HR patients receive PEG-asparaginase once at the end of induction, once in each HR treatment block (7-9 blocks) and twice during DI. From January 2009 until March 2016 at treatment day 92 (after 5 doses of PEG-asparaginase at 2 weeks intervals) non-HR Nordic children (85% of all Nordic children with ALL) were offered a randomization

between continuous and intermittent PEG-asparaginase treatment (given every 2nd or every 6th weeks, respectively).

The randomization was closed March 1st 2016 and non-HR patients are now treated according to the previous experimental arm (i.e. PEG-asparaginase every 6w from day 92). Manuscript of the results of the randomization is in preparation.

In ALLTogether pilot protocol PEG-asparaginase (1500 I.E./m² i.v. <16 years, and 1000 I.E./m² i.v. ≥16 years) is given from treatment day 4 and repeated at 2-week intervals. The non-high risk group consists of three treatment groups after stratification day 29, i.e. very-low risk, intermediate low risk and intermediate high risk and receiving 4, 5 and 8 doses, respectively. Therapeutic drug monitoring are done routinely to identify enzyme inactivation (silent or in combination with hypersensitivity reactions). Optimization of asparaginase treatment is considered one of the major focus areas in the ALLTogether protocol.

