The use of PEG-asparaginase are compromised by frequent and significant toxicities, such as clinical allergic reactions, pancreatitis, and thrombosis. Clinical allergy is the most frequent serious adverse event observed. In total, 13% of the patients (~30/year) treated on the NOPHO ALL 2008 protocol develop allergy to PEG-asparaginase (7). The majority (85%) of the Nordic ALL2008 childhood ALL patients who developed allergy, did so after the 2nd or 3rd dose and are thus potentially undertreated because further doses are impossible.

Truncated asparaginase therapy is associated with inferior event-free survival outcomes, in particular CNS relapse. It is well known that insufficient CSF asparagine depletion is a concern and is correlated with ineffective killing of leukemic cells in the CNS. CNS may serve as a sanctuary for leukemic cells, and consequently this may increase the risk of CNS relapse despite other CNS-directed therapy. Truncated L-asparaginase treatment has been associated with increased risk of CNS relapse (8-10).

The impact of asparaginase truncation due to clinical allergy may depend on the timing of the allergic event (10). Data from NOPHO ALL 2008 protocol (manuscript in preparation) indicates that there retrospectively is no asparaginase-activity from start of treatment in patients who later develop clinical allergy. This means that patients with hypersensitivity reactions have no effect of the treatment with asparaginase at all.

In addition, loss of enzymatic efficacy - "silent inactivation" are found in 5-6% of the patients who receive conventional PEG-asparaginase treatment. It is observed as a consequence of the production of symptom-free serum antibodies directed to the asparaginase and blocking its pharmacological activity. These patients have no effect of the asparaginase treatment as well. (Manuscript in preparation).

After an allergic reaction, non-HR patients are treated with Erwinase (20.000 IU/m² 3 times a week for two weeks) during Delayed Intensification, and HR patients during the subsequent blocks and DI. Erwinase has a short half-life (7-16 hrs), thus frequent administration is necessary. There is a need for an effective alternative preparation with a longer half-life for PEG-asparaginase allergic patients. In the current NOPHO ALL 2008, protocol PEG-asparaginase treatment is only replaced for 2 weeks and further scheduled doses are cancelled. The importance of the treatment with asparaginase is so

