7.6 Dose interruption and modification

Temporarily dose interruption in case of following:

- Severe hepatic impairment (transaminases >10 times ULN).
- Bilirubin > ULN and other clinical signs of SOD (according to the PdL consensus definitions)
- Serious infectious disease

Treatment can be resumed when parameters are normalized and the clinical condition allows further treatment. Impact of hematological parameters will not induce dose interruption.

Eryaspase treatment is discontinued in case of:

- Clinical allergy of any grade
- Pancreatitis
- Serious hemorrhage or serious thrombosis
- No asparaginase activity

There will be no dose-modification due to haematological or non-hematological toxicities only temporarily dose interruption or discontinuation of the eryaspase treatment.

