2.4. Secondary Endpoints

2.4.1. Pharmacokinetic Evaluation:

2.4.1.1. Key Secondary Endpoint:

- The percentage of patients with ASNase activity >100 U/L at 14 days following the *fourth* infusion of the 2-week dosing intervals.

Sponsor:	NOPHO – Nordic Society of Pediatric Hematology & Oncology		
Protocol:	NOR-GRASPALL 2016		
Document Version No.:	2.0	Document Date:	14-May-2021

2.4.2. Pharmacodynamic Evaluation:

- Cerebrospinal fluid (CSF) concentrations of asparagine (ASN), aspartate (ASP), glutamine (GLN), and glutamate (GLU)

2.4.3. Immunogenicity:

- Anti-asparaginase antibodies.

2.4.4. Safety and Tolerability:

- Incidence of hypersensitivity (allergic reactions and silent inactivation);
- Adverse events from start of treatment until 30 days after last administration;
- Levels of cytotoxic methotrexate (MTX polyglutamates) and 6 mercaptopurine metabolites (6 thioguanine nucleotides (6TGN) and methylated metabolites (MeMP)) and of DNA-TGN levels in circulating leukocytes.

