4. GENERAL STATISTICAL CONSIDERATIONS AND DATA HANDLING

4.1. Sample Size Justification

The trial is powered to test the hypothesis that 70% of patients meet the >100 U/L threshold compared to the null hypothesis that this threshold is achieved in 50% of patients. The null and alternative hypotheses stated here align with those outlined in previous FDA approvals, such as CDER Application (125359Orig1s000) for Erwinaze in the treatment of ALL. Based on a one-sided significance level of 2.5%, a total of 49 patients will provide 80% power for this comparison in an exact binomial test. A total of 55 patients will be recruited to allow for a ~10% dropout rate for an analysis based on evaluable patients.

Originally, the study was planned for 30 patients. An interim analysis was conducted after first 18 patients enrolled into the study, and study continued to enroll all 35 patients. The protocol was amended in August 2019 to increase the sample size up to 55 patients. The sample size increase was prompted by:

1. Continuous Erwinaze shortage and the need to complete the intended courses of asparaginase therapy
2. Encouraging safety and efficacy profile based on the informal interim analysis in the first 18 patients
3. Note that the sample size increase was not based on any evaluation of the primary endpoint from the study data collected up to that point

The primary population for analysis will be the Evaluable Patient population defined as all patients recruited into the study who provide data on whole blood ASNase activity on Day 14 (+/- 2 days) following the first administration of eryaspase.

A formal statistical hypothesis test will be performed on the primary endpoint. A single sample binomial test will be used to test the null hypothesis at the 2.5% one-sided significance level. The key secondary endpoint with the threshold of 100 U/L following the fourth infusion will be evaluated in the same way. Multiplicity will be controlled across the primary and key secondary endpoint through a pre-specified hierarchy with the primary endpoint in position 1 and the key secondary endpoint in position 2.

Descriptive statistics will be presented. For binary endpoints, 95% confidence intervals for the observed proportions will be calculated using Wilson Score method.

Sponsor:	NOPHO – Nordic Society of Pediatric Hematology & Oncology		
Protocol:	NOR-GRASPALL 2016		
Document Version No.:	2.0	Document Date:	14-May-2021

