4.2. General Methods

The primary statistical analyses will be performed using cleaned eCRF data.

All output will be incorporated into Microsoft Excel or Word files, sorted and labeled according to the International Conference on Harmonisation (ICH) recommendations, and formatted to the appropriate page size(s).

Tabulations will be produced for appropriate demographic, baseline, efficacy, pharmacokinetic and safety parameters. For categorical variables, summary tabulations of the number and percentage within each category (with a category for missing data) of the parameter will be presented. For continuous variables, the mean, median, standard deviation, minimum and maximum values will be presented. Time to event data will be summarized using Kaplan-Meier Methodology using 25th, 50th (median), and 75th percentiles with associated 2-sided 95% confidence intervals, as well as percent of censored observations.

The following general data handling conventions, will be used in derivation of variables used in data summaries and analysis:

Term	Definition/Rule
Date of diagnosis of ALL	Date of initial ALL diagnosis
Start date of exposure period	Start date of eryaspase treatment
End date of exposure period	The end date of treatment exposure is defined as follows, depending the one occurs first: 
 • 30 days after the last treatment administration • relapse • Death
Study Day	(date of assessment) - (date of first study drug dose) + 1
Months	Study days divided by 30.4375 days
Years	Study days divided by 365.25 days
Baseline	The latest measurement performed during screening and prior to the first dose of study drug. If the baseline value is missing, then the latest non-missing value generated prior to first dose of study drug will be used as the baseline value
Time to Event (i.e., RFS or EFS)	(date of the event) - (randomization date) + 1
Age	(date of informed consent - date of birth)/365.25 rounded down

Sponsor:	NOPHO – Nordic Society of Pediatric Hematology & Oncology		
Protocol:	NOR-GRASPALL 2016		
Document Version No.:	2.0	Document Date:	14-May-2021

Term	Definition/Rule
Date of diagnosis of ALL	Date of initial ALL diagnosis
Total duration of treatment	(date of last dose) – (date of first dose) + 1

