4.6.1. Evaluable Patients (EP) Population

This is the primary population for the analysis of the primary and key secondary endpoint(s), defined as all patients recruited into the study who provide data on asparaginase level on Day 14 (+/- 2 days) following the first administration of eryaspase.

The evaluation of the secondary endpoints will also be based on this population but without any imputation for missing data.

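### Testing the infusion-4 endpoint on observed cases drops patients stopped for no asparaginase activity, which biases the percentage above 100 U/L upward

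*SAP*

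**What the plan says.** SAP 2.4.1.1 places the key secondary endpoint 14 days after the fourth "infusion of the 2-week dosing intervals". SAP 4.1 sets a null of 50% and a one-sided 2.5% exact binomial test for the primary endpoint, and adds: "The key secondary endpoint with the threshold of 100 U/L following the fourth infusion will be evaluated in the same way". The key secondary endpoint stands second in the hierarchy.

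SAP 4.6.1 names Evaluable Patients as the population for both endpoints. Membership depends on a Day 14 (±2 days) value after the first infusion; nothing is required after the fourth. A second sentence in 4.6.1 says that the secondary endpoints use the same population with no missing values filled in.

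SAP 4.11 makes no substitutions for missing data in general, and 4.11.1 is specific: "Missing asparaginase activity data will not be replaced or imputed".

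Protocol 7.6 lists "No asparaginase activity" among the reasons for discontinuing eryaspase, next to clinical allergy of any grade. Protocol 11.1 also lists lack of activity as a reason to stop. Planned eryaspase doses range from 1 to 7 (Protocol 5.1, SAP 3.1), so not every patient is due a fourth 2-week infusion.

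**The concern.** An Evaluable Patient can lack an infusion-4 value for two quite different reasons. Some were never scheduled for a fourth 2-week infusion, and for them the endpoint does not apply. Others were scheduled but were stopped first because the enzyme showed no activity. For this second group the reason the value is missing is itself the answer: the patient did not keep activity above 100 U/L. An analysis that uses only measured infusion-4 values treats both groups alike and removes both.

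Removing the never-due patients is reasonable. Removing the no-activity stops takes failures out of the denominator and leaves the numerator unchanged, so the percentage can only go up. This is a formally tested endpoint, and an infusion-4 percentage close to the infusion-1 percentage could be read as sustained activity when part of the agreement comes from patients having left.

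Patients with quantifiable activity at or below 100 U/L are not stopped under Protocol 7.6. They stay in the denominator as failures, so the bias concerns only those with no activity.

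**Working it through.** **The plan's own figure.** SAP 4.1 gives 49 evaluable patients for 80% power, 50% against 70%, one-sided 2.5%, exact binomial. P(X ≥ 32 | 49, 0.5) = 0.0222 and P(X ≥ 31 | 49, 0.5) = 0.0427, so the test rejects at 32 or more. P(X ≥ 32 | 49, 0.7) = 0.810. The figure reproduces.

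**Direction and size of the bias.** Let r be the true share above 100 U/L among patients due a fourth 2-week infusion, with no-activity stops counted as failures. Let f be the share of those patients stopped for no activity before the sample. With no other missing values, the observed-case share is r/(1 − f). At r = 50%:

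- f = 5%: 0.50/0.95 = 52.6%
- f = 10%: 0.50/0.90 = 55.6%
- f = 20%: 0.50/0.80 = 62.5%

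**Effect on the test.** N is the number due a fourth infusion. Patients sampled: n ~ Binomial(N, 1 − f). Responders: Binomial(n, 0.5/(1 − f)). The exact one-sided 2.5% test against 50% is applied to n. Chance of rejecting, given that the hierarchy reaches this test:

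| N | f = 0 | f = 5% | f = 10% | f = 20% |
|---|---|---|---|---|
| 10 | 1.1% | 1.9% | 2.8% | 5.2% |
| 15 | 1.8% | 2.1% | 3.1% | 7.9% |
| 20 | 2.1% | 2.7% | 4.6% | 11.9% |
| 49 (upper bound) | 2.2% | 4.0% | 8.7% | 29.2% |

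**What the documents say about N and f.** They give neither, so both are assumptions.

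- *N, NOPHO ALL 2008.* Protocol 1.0 puts the earlier randomisation "after 5 doses of PEG-asparaginase at 2 weeks intervals". If the reacting dose counts as given, a reaction at PEG dose 1, 2 or 3 leaves 4, 3 or 2 two-weekly slots, and one more if that dose is replaced. Of the NOPHO children with allergy, 85% "did so after the 2nd or 3rd dose and are thus potentially undertreated".
- *N, ALLTogether.* Protocol 7.4.2 gives 4, 5 or 8 asparaginase doses by risk group. After one PEG dose, 3, 4 or 7 remain. An intermediate-high patient who reacts at dose 3 still has 8 − 3 = 5.
- *f.* No rate of no-activity stops on eryaspase is given. The nearest figure is 11.5% in Protocol 2.1.2, but that is allergy incidence in another trial with no withdrawals for hypersensitivity. It does not estimate f.

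**Illustration (assumed counts).** 20 due; 14 above 100 U/L, 4 measured at or below it, 2 stopped for no activity (f = 10%).

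- Observed cases: 14/18 = 78%, p = 4048/2^18 = 0.015; rejects.
- Stops as failures: 14/20 = 70%, p = 60460/2^20 = 0.058; does not reject.

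**Second illustration (assumed counts).** 49 Evaluable Patients, 10 never due, 5 stopped for no activity, 24 of the 34 sampled above. Observed cases: 24/34 = 70.6%, p = 0.012. Stops as failures: 24/39 = 61.5%, p = 0.100.

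**The case against.** The strongest reply is that the bias is measured against an estimand the SAP never adopted. The endpoint is activity 14 days after the fourth infusion. If the target is patients who received that infusion, the exact test on observed cases holds its 2.5% level and nothing is inflated. That is correct for that conditional question. But the SAP assigns the endpoint to Evaluable Patients and does not state a population conditional on receiving infusion 4. A result limited to patients who kept activity long enough to be dosed again also says little about sustained activity.

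Several mitigations stand. A patient with no activity at the Day 14 sample of infusion 1 already counts as a failure of the primary endpoint. Hypersensitivity, including silent inactivation, is a separate secondary endpoint (SAP 2.4.4). SAP 5.1 tabulates doses completed and reasons for stopping, so attrition would be visible, although its listed reasons do not name lack of activity. The test is reached only if the primary succeeds.

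A reader might infer more than the documents support:

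- *That no denominator is stated at all.* SAP 4.6.1 does name the population. What is missing is the rule for its members who have no infusion-4 value.
- *That the test may be impossible to pass, because all Evaluable Patients count and 32 of 49 are needed.* This reading would wrongly fail patients who were never due a fourth infusion. It rests mainly on SAP 4.2, which tabulates categorical variables "with a category for missing data", and it conflicts with 4.11 and 4.11.1. The second sentence of 4.6.1 leaves some doubt whether imputation was meant for the key secondary endpoint, but none is defined.
- *That few patients can be due a fourth infusion.* This follows from the NOPHO schedule alone and overlooks ALLTogether intermediate-high patients. The split between protocols is not given.
- *That allergy stops must be failures.* That is an estimand choice the SAP has not made.

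**Conclusion.** The concern holds for no-activity stops. As written, the plan leads naturally to an observed-case test from which patients who failed the endpoint have been removed, and the direction is always upward. It affects the key secondary endpoint; the primary is untouched.

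The size cannot be fixed from the documents. With 10 to 20 patients due a fourth infusion, rejection at a true 50% is 1.9% to 2.7% when 5% are stopped for no activity, which is no material excess. It is 2.8% to 4.6% at 10% stopped and 5.2% to 11.9% at 20%. The N = 49 row assumes that every patient in an evaluable set of the planned size is due a fourth infusion, so it is only an upper bound. All these figures rest on assumed N and f, on no other missing values, and on counting a no-activity stop as a failure. The illustrations show that two to five such patients can decide the result.

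This should be corrected, but it does not threaten the trial's main conclusion.

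**What to change.** Add to SAP 4.1 and 4.6.1:

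> *The key secondary endpoint is analysed in Evaluable Patients whose remaining schedule at the first eryaspase dose included at least four 2-week infusions. A patient discontinued before the infusion-4 Day 14 sample for no asparaginase activity counts as not >100 U/L. Other missing infusion-4 values are excluded and reported by reason. Sensitivity analyses: (a) allergy stops counted as not >100 U/L; (b) all missing values counted as not >100 U/L; (c) observed cases.*

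In SAP 5.1, list lack of asparaginase activity as a separate reason for stopping.

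No new data collection is needed. Protocol 11.1 already puts the reason and date of early withdrawal on the CRF, and Protocol 9.1 records the risk group at screening. There is some derivation work: SAP 7.3 uses planned infusions in total, so the number of planned 2-week infusions must be worked out for each patient from the treatment protocol, risk group and time of switch.

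The price is a percentage that may be lower than the observed-case figure and may lose significance, as in the 14/20 illustration. The text should be in place before hard database lock. After lock it can only be a labelled supplementary analysis in the clinical study report.

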4.11.2. Adverse Events

For missing or partial missing onset dates for adverse events, the following conventions will apply to determine whether an AE is treatment-emergent:

- If the start date of an event is completely missing, then the event is assumed to be treatment-emergent.

Sponsor:	NOPHO – Nordic Society of Pediatric Hematology & Oncology		
Protocol:	NOR-GRASPALL 2016		
Document Version No.:	2.0	Document Date:	14-May-2021

- If the start date has the month and year but day is missing, the event will be considered treatment-emergent if the month and year of the start date of the event are equal to, or greater than, the month and year of the date of first dose of study drug.
- If the start date has the year, but day and month are missing, the event will be considered treatment-emergent if the year of the start date of the event is to the same as, or later than, the year of the date of the first dose of study drug

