5.0 STUDY DESIGN

5.1 Study Overview

This is a single arm, multicenter, multinational study to assess the pharmacological activity, safety and immunogenicity of eryaspase in combination with the NOPHO ALL 2008 or ALLTogether pilot protocol chemotherapy protocol administered as second line treatment to children or adult patients from 1 to 45 years old with ALL who experience hypersensitivity reactions (clinical allergic reaction or silent inactivation) to PEG-asparaginase.

[figure not shown]
All patients will receive the NOPHO ALL 2008 or ALLTogether pilot protocol chemotherapy regimen, which consists of an induction treatment, consolidation, delayed intensification phase and maintenance phases, a CNS prophylaxis and interim maintenance for a total of 30 months' treatment duration. Once a patient presents with hypersensitivity to PEG-asparaginase, eryaspase will be given as a replacement therapy for remaining scheduled PEG-asparaginase administrations (Figure 3).

FIGURE 3A. STUDY DIAGRAM – PATIENTS TREATED ACCORDING TO NOPHO ALL 2008:

Erytech internal code GRASPALL 2016-12

FIGURE 4B. STUDY DIAGRAM – PATIENTS TREATED ACCORDING TO ALLTOGETHER PILOT PROTOCOL:

*According to ALLTOGETHER protocol: VLR: 4 doses IR low: 5 doses IR high: 8 doses

Erytech internal code GRASPALL 2016-12

Eryaspase will be administered every 2 weeks for a maximum of 4 doses. Then administered every 6 weeks for 3 doses to the end of planned treatment according to the NOPHO ALL 2008 or ALLTogether pilot protocol.

Assessments include overall safety profile of eryaspase, PK/PD parameters of eryaspase, immunogenicity of eryaspase, during successive courses of treatment with eryaspase.

Primary trial assessments for each patient will continue for 1 month following the end of the planned eryaspase treatment phases (approximately 6 months in case of 7 doses). Each patient will receive cytostatic treatment in about 22 months after last administration of eryaspase according to the NOPHO ALL 2008 or ALLTogether pilot protocol. After cessation of therapy patients will be followed for recurrence of disease or the development of late effects. The follow-up after cessation of therapy should be done according to guidelines on each country and site and includes no assessments for this study. Further details regarding the study assessments during the study are provided in section 9.0.

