- Anemia: Anemia, hemoglobin decreased
- Thrombocytopenia: Thrombocytopenia, platelet count decreased
- Leukopenia: Leukopenia, white blood cells count decreased
- Leukocytosis: Leukocytosis, white blood cells count increased
- Hyperglycemia/Diabetes: Hyperglycemia, Diabetes mellitus, Diabetes mellitus inadequate control, Type 2 diabetes mellitus, blood glucose level increased
- Hypertriglyceridemia: Hypertriglyceridemia, triglycerides increased
- Hepatotoxicity: Liver injury, drug-induced liver injury, hepatocellular injury, Venoocclusive liver disease
- Hyperuricemia: Hyperuricemia, blood uric acid increased
- Hypokalemia: Blood potassium decreased, hypokalemia
- Hyponatremia: Blood sodium decreased, hyponatremia
- Hypocalcemia: Blood calcium decreased, hypocalcemia
- Pancreatitis: Pancreatitis, Acute pancreatitis
- Biochemical pancreatitis: Lipase increased, Amylase increased, pancreatic enzymes increased
- Drug hypersensitivity reaction: Drug hypersensitivity, hypersensitivity, anaphylactic reaction, anaphylactic shock, erythema multiform, edema, dermatitis allergic, face edema
- 4. Other allergic reaction: Rash, Erythema multiform, Food allergy, Anaphylactic shock, Transfusion reactions, Angioedema, allergic transfusion reaction.

All AEs and SAEs will be collected and reported in the patient's eCRF throughout study duration (i.e. for time subject signs the informed consent and until 30 days after last administration of eryaspase or chemotherapy. All AEs along with the coded terms will be listed.

The following general rules apply to adverse events:

Sponsor:	NOPHO – Nordic Society of Pediatric Hematology & Oncology		
Protocol:	NOR-GRASPALL 2016		
Document Version No.:	2.0	Document Date:	14-May-2021

- TEAEs are defined as those AEs that started on or after the first dose of study medication or that worsened after the first dose of study medication and with an onset date occurring during the treatment period.
- Treatment period is defined from the first dosing day of study treatment (minimum of the first dosing day for eryaspase (Day 1) until 30 days after last dose of study treatment (maximum of the last dosing day for eryaspase). This includes the safety follow-up period as well.
- If an AE is reported for a given patient more than once during treatment, the worst severity and the worst relationship to study treatment will be tabulated.

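### The SAP's rules for incomplete AE onset dates omit the 30-day upper limit and the stop date, so some events already known to lie outside the treatment period are counted as treatment-emergent

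*SAP*

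**What the plan says.** SAP 4.11.2 gives three rules for deciding whether an AE with a missing or partial onset date is treatment-emergent:

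- Nothing recorded: "If the start date of an event is completely missing, then the event is assumed to be treatment-emergent".
- Day missing: treatment-emergent if "the month and year of the start date of the event are equal to, or greater than, the month and year" of the first dose.
- Day and month missing: treatment-emergent if "the year of the start date of the event is to the same as, or later than, the year" of the first dose.

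SAP 8.1 defines a treatment-emergent AE as one that started on or after the first dose, or that "worsened after the first dose of study medication and with an onset date occurring during the treatment period". The treatment period runs from the first eryaspase dose "until 30 days after last dose of study treatment", and the same sentence ties that last dose to eryaspase.

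The documents give two AE collection windows. SAP 8.1 collects events "for time subject signs the informed consent and until 30 days after last administration of eryaspase or chemotherapy". SAP 2.4.4 and Protocol 4.4 instead run from the start of treatment to 30 days past the last administration. Protocol 10.0 has the same end point and defines an AE as something occurring after the infusion.

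**The concern.** The definition in SAP 8.1 has a lower and an upper limit; the rules in SAP 4.11.2 have a lower limit or none. For some events the recorded month, year or stop date already settles that onset was outside the treatment period, and the rules still return treatment-emergent. The same event with its day filled in would be excluded.

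Counting an uncertain onset as treatment-emergent is a normal cautious default. These cases are not uncertain. An event that had ended before the first dose cannot have started or worsened after it, and an event dated to a month wholly beyond the 30-day limit cannot have begun within it. Elsewhere the SAP does use such information: its medical history section (5.2.3) lets a partial end date place a condition before the selection visit.

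At stake is the treatment-emergent AE summary of a single-arm study with concurrent chemotherapy. SAP 8.1 presents AEs primarily without regard to causality, so the time window does much of the work of tying events to eryaspase.

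**Working it through.** The plan gives no figure on this point to reproduce. The check applies both sections to the same events and then asks how often such events could be in the database.

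**Inputs.** Rules: SAP 4.11.2. Limits: SAP 8.1. Schedule: one dose, or four two-weekly doses alone or followed by three at six-week intervals (Protocol 7.4.2). First dose on 20 March 2019 is an assumption, for illustration only.

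**End of treatment period = last dose + 30 days.**

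- One dose: 0 + 30 = 30 days after first dose, 19 April 2019.
- Four two-weekly doses: 3 × 14 = 42; 42 + 30 = 72 days, 31 May 2019.
- Seven doses, fifth given six weeks after the fourth: 42 + 3 × 42 = 168; 168 + 30 = 198 days, 4 October 2019. If the fifth came two weeks after the fourth, 42 + 14 + 84 + 30 = 170 days, which is earlier.

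**Test events, valid for all of these schedules.**

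| Recorded onset | Recorded stop | SAP 4.11.2 | SAP 8.1 limits applied to what is known |
|---|---|---|---|
| Dec 2019, no day | none | emergent | wholly after the period: not emergent |
| Mar 2020, no day | none | emergent | wholly after: not emergent |
| 2020 only | none | emergent | wholly after: not emergent |
| Mar 2019, no day | 15 Mar 2019 | emergent | ended before first dose: not emergent |
| 2019 only | 15 Mar 2019 | emergent | ended before first dose: not emergent |
| nothing | 15 Mar 2019 | emergent | ended before first dose: not emergent |
| Apr 2019, no day (control) | none | emergent | may be inside: emergent |

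All six problem cases are called emergent by SAP 4.11.2 and none by the bounded reading. The control is unchanged.

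**How far this reaches depends on the collection window.**

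- Protocol 4.4 and 10.0 and SAP 2.4.4: collection coincides with the treatment period, so the share of collection time outside it is about 0.
- SAP 8.1, collection "until 30 days after last administration of eryaspase or chemotherapy": Protocol 5.1 states "Each patient will receive cytostatic treatment in about 22 months after last administration of eryaspase". With the SAP's 30.4375 days per month, 22 × 30.4375 = 669.6 days of chemotherapy, and 669.6 + 30 = 699.6 days of collection after the last eryaspase dose. After one infusion, 669.6 / 699.6 = 95.7% lies outside. After seven doses over 168 days, 669.6 / (168 + 699.6) = 77.2%.
- Before the first dose, SAP 8.1 wording only: the protocol synopsis puts screening at up to 8 days. An event starting 1 to 8 days before the first dose starts on average 4.5 days before it, so it shares the first-dose calendar month with probability about 1 − 4.5 / 30.4375 = 85%, assuming both dates are evenly spread. If its day is missing, the second rule then calls it emergent.

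Except for that 85%, which is a probability for a single event, these are shares of calendar time, not of events. For scale, one extra patient with an event adds 1/55 = 1.8 to 1/50 = 2.0 percentage points to an incidence, using the planned totals in the SAP (55) and protocol (50).

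**The case against.** **Few such events should exist.** Under Protocol 10.0 an event before the first infusion is not an AE, registration ends 30 days after the last administration, and events unrelated to eryaspase are not entered in the CRF. Protocol 13.1 has missing and ambiguous data queried. The wider wording in SAP 8.1 conflicts with these sections and with SAP 2.4.4. This stands, and it limits the size of the problem. It does not make the rule right, because the SAP that governs the analysis also states the wider window.

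**A reader might infer that 96% of a patient's AE collection time, or some 700 days, is exposed.** The documents do not support that as a general figure. It needs the SAP 8.1 collection wording and a single infusion, and 22 + 1 = 23 months after the last dose exceeds the roughly 1.5 years on study in the protocol synopsis. It is an upper extreme, with about zero at the other end.

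**A reader might infer that eryaspase rates are always inflated.** They are not. SAP 8.1 counts a patient once per preferred term, so an extra event may change nothing, and treatment-related events are also tabulated separately. Misclassification can leave the number of patients with a given event unchanged or raise it; it cannot lower it. Because the worst severity is tabulated, it may also move a patient to a higher grade.

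**SAP 4.11.2 could be read as settling only the lower boundary, with SAP 8.1 still supplying the upper one.** That is a sensible intention, but the rules state a final classification, and SAP 8.1 does not say how to test its upper limit on an incomplete date. Even on that reading, the stop date remains unused in SAP 4.11.2. The remark in SAP 4.11 that another rule will be used on conflict names no rule and belongs to the imputed-date convention, so it does not close the gap.

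**Conclusion.** The point holds, as a minor defect. SAP 4.11.2 classifies some events as treatment-emergent that SAP 8.1 would exclude if the date were complete: those whose known month or year lies wholly past the 30-day limit, and those known to have stopped before the first dose. Only AEs with incomplete onset dates are touched, and the documents do not say how many there are, so no effect on any rate can be stated. The effect should be small if data were collected under the protocol and SAP 2.4.4 window, and larger only under the SAP 8.1 wording. The primary endpoint is not affected.

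This assumes that the onset condition in SAP 8.1 governs new as well as worsened events. The sentence could be parsed otherwise, but the 30-day limit in SAP 2.4.4 supports this reading.

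**What to change.** Keep the first-dose comparisons in the second and third rules of SAP 4.11.2, and add one sentence applying to all three rules:

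> An event with a missing or partial start date is not treatment-emergent if (a) its stop date, as far as known, is before the first dose, or (b) the known month and year (or year) of onset lies entirely after 30 days following the last eryaspase dose; cases that remain ambiguous are treated as treatment-emergent.

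The sentence must supplement the existing lower-limit tests, not replace them. An ongoing event with onset in January 2019 and a first dose on 20 March 2019 is not treatment-emergent under the second rule now, and must stay so.

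In the same revision, reconcile the AE collection windows in Protocol 10.0, SAP 2.4.4 and SAP 8.1, and state which one the data were collected under.

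The cost is one sentence in the SAP, two conditions in the AE derivation, and one wording correction for the windows. No new data are needed, and the cautious default is kept for events that are truly uncertain.
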